TR Istanbul University-Cerrahpaşa ID: İstanbulUCEdu **Study Protocol: June 1, 2023** the effect of two different bathing methods on vital parameters oath stress levels in preterm babies. Clinical Trial Number: NCT06166485

WORKING PROTOCOL	
Title / Date	The effect of bathing applied in two different orders on stress level and physiological parameters in term babies / 01.06.2023
Approval of the education officer of the unit(s) where the study will be carried out.	Newborn Clinic
Name and surname of the responsible investigator, e-mail address, mobile phone, signature	Prof. dr . [name] [contact] [name]
Assistant researcher name and surname, e-mail address, mobile phone, signature	[name] [contact] [name]
Assistant researcher name and surname, e-mail address, mobile phone, signature	
Financial agreements between the sponsor, principal investigator or research site	
main purpose, Secondary purpose, if any hypothesis ( es )	Main Purpose: This study was planned to determine the effect of bathing applied in two different orders (first the body and then the head, and the classical method of washing the whole body, starting from the head) on the stress level and physiological parameters of term babies.  Hypotheses:  -H0 Stress levels and physiological parameters of babies are similar in bathing methods performed from head to toe or head to toe.  -H1. Babies' stress levels are higher when bathing in a sequence from head to toe compared to bathing where the head is left until the end.  -H2. When bathing is performed in a sequence from head to toe, the baby's physiological parameters are more negatively affected than when the bath is left from head to end.  -H3. In the bathing method in which the head is washed first, the time for babies to calm down is longer than in the method in which the head is washed last.  -H4. The procedure time in the bath where the head is left last is shorter than in the bath method where the head is washed first.
Medical condition/area of treatment investigated	In this study; The effect of bathtub baths applied in two different orders of the stress level and physiological parameters of term babies will be investigated. No treatment will be applied. The research to be conducted is one of the baby care practices that are among the independent functions of the researchers who will conduct the research. The effect of baby bath applied with two different methods on healthy babies' stress level, physiological parameters, babies' calming time and procedure time will be investigated.

of the population to be examined (acceptance and exclusion criteria, age range by gender, termination criteria of the study when necessary) identification of subgroups, if any )	Criteria for inclusion in the research;  The baby's body weight is between 2.5 - 4 kg  The baby's Apgar score is >7  The baby does not have any health problems  Their parents agree to participate in the study  Determined as a healthy term baby  Exclusion criteria from the study;  Meconium aspiration etc. washed immediately after birth for various reasons,  Having various health problems,  Their parents did not agree to participate in the study,  It was decided to exclude low birth weight and premature babies from the scope of the research.  Independent variables;  Traditional bathtub bathing from head to toe and bathtub bathing methods where the head is left last  Dependent variables;  Stress level of babies, physiological parameters (body temperature, pulse, respiration, O 2 saturation), procedure time (bathing time), time for babies to calm down
Design features (clinical trial / retrospective study / case) sample size, determination of the number of centers, study duration, if any randomization method and its importance Blindness method and its importance, if any	This study was planned as a randomized controlled experimental study. Computer-assisted randomization will be used to create groups (https://www.randomizer.org/). To determine the sample size, power analysis was performed using the $G^*$ Power (v3. 1.9) program. The power of the study is expressed as 1- $\beta$ ( $\beta$ = probability of type II error), and in general, studies must have 80% power. According to Cohen's (1988) effect size coefficients; Assuming that the evaluations to be made between two independent groups would have a medium effect size (d = 0.5), it was determined that there should be at least 64 people in each group, according to the calculation made using the t test.
Address of the clinic, laboratory, other medical units and institutions, if any, from cases, processing of data/keeping records, evaluation criteria, quality control and quality assurance	No samples will be taken from the babies forming the sample group.
Statistical method to be applied	The data obtained in the study were compiled using SPSS (Statistical Package for Social Sciences ) for Windows 25.0 program. In evaluating the data; Descriptive statistical methods will be used for number, percentage, min-max, mean and standard deviation values.  The compliance of the obtained data with normal distribution will be tested. Compliance with normal distribution can be examined with the QQ Plot drawing (Chan, 2003:280-285). In addition, normal distribution of the data used depends on the skewness and kurtosis values being between ±3 (Shao, 2002).  In normally distributed data, when comparing quantitative data, independent t test will be applied for the difference between two independent groups, when comparing two dependent stages, dependent t test will be applied, and when comparing more than two dependent stages, analysis of variance in repeated measurements (MIX ANOVA) will be applied and in case of a difference, Bonferroni will be applied to determine the group that makes the difference. will be used. Chi square analysis will be used to test the relationship between categorical variables.

- Kuller, J. M. (2014). Update on newborn bathing \_ newborn oath baby Nursing Reviews, 14(4), 166-170.

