TR Istanbul University-Cerrahpaşa ID: İstanbul UCEdu

Statistical Analysis Plan: June 1, 2023 The effect of two different bathing methods on vital parameters and stress levels in preterm babies.

Clinical Trial Number: NCT06166485

BIOSTATISTICS PRELIMINARY ASSESSMENT

The thesis summary and research hypotheses of the thesis titled "The effect of bathing applied in two different orders on the stress level and physiological parameters in term babies" were examined in detail. For this purpose, mothers who applied to the gynecology clinic of Istanbul Şişli Hamidiye Etfal Training and Research Hospital, whose weight was between 2.5 and 4 kg, whose Apgar score was over 7 points, who did not have any health problems, who were healthy term babies, and who voluntarily agreed to participate in the study. and their children will be included. As a data collection tool;

- Personal information form,
- Processing time (time to get the bath done),
- Babies' calm down time,
- newborn stress scale,
- Physiological parameters (body temperature, pulse, respiration, O2 saturation) will be used.

Data from IBM SPSS Statistics Standard Concurrent User V 26 (IBM Corp. , Armonk , New York, USA) will be evaluated in the statistical package program. Descriptive statistics will be given as number of units (n), percentage (%), mean \pm standard deviation ($Mean\pm SD$), median (M), minimum (min) and maximum (max) values. Shapiro-Wilk normality test will be used to ensure that numerical variables comply with normal distribution. The appropriate hypothesis testing method planned to be used in the study was determined as "Mixed Pattern Variance Analysis" if parametric test assumptions were met. In cases where the parametric test assumptions regarding the relevant test are not met, whether there is a difference between the groups in terms of quantitative variables will be evaluated with the "Student t test" if the parametric test assumptions are met, and with the "Mann-Whitney test" if the parametric test assumptions are not met. In examining whether the quantitative variables change according to the pre-test and post-test measurement time, they will be examined with the "Paired t test" if the test assumptions are met, and with the "Wilcoxon test" if they are not met. In all hypothesis tests, the probability of Type I error will be taken as α =0.05 and a value of p<0.05 will be considered statistically significant.

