Mohamed et al. $(2018)^{**}$ in their study, they investigated whether bathing applied in two different orders in term babies had an effect on stress level and physiological parameters. Differences between and within groups were calculated for body temperature (°C), heart rate (beats/ min) and oxygen saturation (%). Minimal significant change was observed in the study While the average heart rate (beats/ min) was 145 ± 16.44 points in the training group as a result of the first measurements, it was found to be 138 ± 12.12 points in the last measurement. In the control group, the first measurement was 140 ± 14.22 points and the last measurement was 139 ± 10.88 points. As a result, it was determined that there should be 86 observations in the sample with a statistical power level of 80.4% and a significance level of 5% for the calculated (f=0.128)* effect size. Considering sample loss (10%) such as dropping out of the study, it will be sufficient to work with at least 94 patients. The study was planned to include 47 people in each group.

^{*} COHEN, J., "Statistical Power Analysis for the Behavioral Sciences (Revised ed.)", 1977.

F tests - ANOVA: Repeated measures , within-between interaction

Analysis: A priori : Compute required sample size

Input: Effect size f=0.1275153

> α err prob =0.05=0.80Power $(1-\beta \text{ err prob })$ Number of groups =2Number of measurements =4 corr among rap measures =0.5Nonsphericity correction ϵ =1

Output: Noncentrality parameter λ =11.1869844

Critical F=2.6404222

numerator df = 3.0000000

denominator df = 252 =86 Total sample size

Actual power =0.8044596

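### The protocol requires at least 64 babies per group, the SAP of the same date plans 47, and neither document says which target governs.

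*Protocol*

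**What the plan says.** **Protocol, design features row.** It gives as a general rule that "in general, studies must have 80% power". Taking Cohen's medium effect (d = 0.5) for a comparison of two independent groups by t test, "it was determined that there should be at least 64 people in each group". That makes 128 babies. The row states no alpha, no sidedness and no allowance for loss.

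**Protocol, statistical method row.** For normally distributed data, "independent t test will be applied for the difference between two independent groups". Repeated measurements go to an analysis of variance.

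**SAP, sample-size paragraph and power output.** The calculation is labelled "F tests - ANOVA: Repeated measures , within-between interaction", with f = 0.1275153, 2 groups, 4 measurements and a correlation of 0.5. It gives 86 babies in total at 80.4% power and a 5% significance level. Then: "Considering sample loss (10%) such as dropping out of the study, it will be sufficient to work with at least 94 patients". And: "The study was planned to include 47 people in each group".

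**SAP, analysis methods.** The main method is a mixed-design analysis of variance. Where its assumptions fail, "whether there is a difference between the groups in terms of quantitative variables will be evaluated with the" Student t test or, failing that, the Mann-Whitney test.

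Both documents are dated June 1, 2023 and carry the same trial number. The SAP text is headed "BIOSTATISTICS PRELIMINARY ASSESSMENT", but nothing in either document says that one figure replaces the other.

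**The concern.** The enrolment target decides when recruitment stops, and this trial has two. A team that follows the SAP stops at 94, which is 34 short of the protocol's minimum. A team that follows the protocol goes to 128, beyond what the SAP calls sufficient. Either way, the final number can be said to have been chosen afterwards.

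Power is also at stake. The 80% claimed in the protocol belongs to a two-group t test and does not hold at the SAP's number. This affects any outcome compared between groups by that test. On a natural reading these include calming time and procedure time (hypotheses H3 and H4), though the protocol does not list outcomes by test, so that link is an inference. It also affects any outcome that falls back from the mixed-design analysis to a t test under the SAP.

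**Working it through.** **1. Reproduce the protocol's 64.** Inputs from the protocol: d = 0.5, 80% power, two equal groups, t test. Alpha 0.05 comes from the SAP; two-sided is inferred.

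Power comes from the noncentral t distribution with df = 2n − 2 and noncentrality d × √(n/2). At n = 64 the noncentrality is 0.5 × √32 = 2.828 and the critical t on 126 df is 1.979.

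- n = 63 per group: 79.5%
- n = 64 per group: 80.1%

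So 64 is the minimum for a two-sided test at 0.05. A one-sided test at 0.05 would need only 51 per group, which is why two-sided is inferred.

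**2. Reproduce the SAP's 86.** Inputs from the SAP's power output: f = 0.1275153, 2 groups, m = 4 measurements, correlation ρ = 0.5, ε = 1, alpha 0.05.

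λ = N × f² × m / (1 − ρ) = 86 × 0.01626 × 4 / 0.5 = 11.187. Numerator df = (2 − 1)(4 − 1) = 3; denominator df = (86 − 2)(4 − 1) = 252; critical F = 2.6404.

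- N = 84: 79.4%
- N = 86: 80.4%, matching the SAP's output
- N = 94: 84.2%

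The loss allowance is 86 × 1.10 = 94.6, taken as 94, or 47 per group.

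**3. Size of the gap.**

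| Basis | Protocol | SAP | Difference |
|---|---|---|---|
| Targets as stated | 128 | 94 | 34 |
| Before any loss allowance | 128 | 86 | 42 |
| Protocol raised for 10% loss (64 / 0.9 = 71.1, so 72 per group) | 144 | 94 | 50 |

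**4. The protocol's t test at the SAP's numbers (alpha 0.05).**

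| Per group | d = 0.5, two-sided | d = 0.5, one-sided | d = 0.6, two-sided | d for 80% power, two-sided |
|---|---|---|---|---|
| 64 | 80.1% | 87.9% | 92.0% | 0.50 |
| 47 | 66.9% | 77.7% | 82.1% | 0.58 |
| 43 | 63.0% | 74.4% | 78.5% | 0.61 |

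Here 43 per group is the SAP's evaluable target (86 / 2).

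**5. The protocol's 64 after loss.** 64 × 0.9 = 57.6. Power at d = 0.5, two-sided, is 76.1% with 58 per group and 75.4% with 57.

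**The case against.** The strongest reply is that the two figures need not conflict. Both are worded as minima, so enrolling 128 satisfies both and gives the SAP's interaction test 94.1% power. That is true. But the SAP also calls 94 sufficient and gives 47 per group as the plan, so a team that follows it stops short of the protocol. The preliminary heading weakens the SAP's standing as a final plan, but it does not say that the protocol's figure prevails.

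Second, the loss of power is conditional. The protocol's d = 0.5 is a conventional medium effect, not tied to any outcome or to a smallest important difference, and at d = 0.6 the SAP's 47 per group gives 82.1%. The SAP's main method is the mixed-design analysis, for which 94 babies give 84.2% at the assumed effect. This stands, and it limits the consequence to t-test comparisons at the protocol's own effect size. The t-test figures should not be read across to the Mann-Whitney test, which is used when normality fails and for which no power was computed.

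Third, the numbers are not built alike: 128 has no loss allowance and 94 has one. That is correct. On a like-for-like basis the gap is larger (42 or 50), so 34 does not overstate it.

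Lastly, a 10% loss from 47 per group leaves 42.3, not 43. At 42 per group the t test has 62.0% power. A 10% loss from 94 leaves 84.6 in total, and the interaction test then has 79.4% at 84 or 79.9% at 85. These differences are small and change nothing in the conclusion.

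**Conclusion.** The inconsistency holds and must be fixed. Two current documents with one date and one trial number give targets of 64 and 47 per group, and no text says which governs. Neither figure is an arithmetic error; they come from two separate calculations for different tests and effects.

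If enrolment ends at the SAP's number, a two-group t test at the protocol's effect size has about 67% power at full enrolment and about 63% at the SAP's evaluable target, against the 80% that the protocol sets. This rests on d = 0.5 and on a two-sided 0.05 level, which the protocol does not state. One-sided, the figures are 77.7% and 74.4%, still below 80%. The SAP's interaction test keeps its stated power at its own assumed effect.

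**What to change.** State one target in both documents, with the test and effect that its power refers to.

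**Option A: 47 per group stands.** Remove the protocol's minimum of 64. State that 80.4% power applies only to the SAP's interaction model (f = 0.1275, 4 measurements, correlation 0.5) with 86 evaluable babies. State also that a two-group t test at d = 0.5, two-sided 0.05, has about 67% power at 47 per group and 63% at 43 evaluable, or 80% only for d of about 0.58 to 0.61. Cost: wording in both documents and a less favourable stated power for the two-group tests; no extra babies.

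**Option B: 64 per group stands.** Replace 94 and 47 in the SAP, and state the power left after the SAP's 10% loss (about 76% at 58 per group for d = 0.5). Cost: 34 more babies than the SAP plans. Holding 80% after that loss takes 72 per group (144 in total), which is 50 more.

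Option A is enough to remove the contradiction. Under either option it would help, as a secondary step, to name the main outcome, tie the stated power to the test for that outcome, and state alpha and sidedness in the protocol.

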journal for Specialists in Pediatric Nursing, 23(1), e12202. -Ceylan, S. S. , & BOLIŞIK, B. (2017). Newborn Stress Scale Examination of Psychometric Properties. Acıbadem University Journal of Health Sciences, (2), 97-103. Relevant sources have been added to the bibliography file. So et al. in 2014, investigating the effect of trunk-to-head bathing on the body temperature, heart rate and oxygen saturation of newborns compared to traditional head-to-torso bathing, it was found that stable and healthy term newborns bathed from trunk to head had lower body temperature before bathing than those bathed from head to trunk. It has been determined that they return to their temperatures faster (So, HS et al. 2014). In 2014, by Edraki et al., 50 premature babies in the neonatal intensive care unit were divided into two groups, experimental and control, by random distribution method. The babies in the experimental group were washed with the swaddle bath method, and the babies in the control group were washed with the traditional bath method. Body temperature was measured 10 minutes before and 10 minutes after bathing. Babies' faces were filmed during bathing to record their cries. The average temperature loss in newborns bathed with swaddle baths was lower than those bathed with traditional bathing methods. It was found to be significantly less than in newborns. Additionally, it was observed that the duration of crying was Summary of findings from significantly less in the experimental group than in the control group. Considering the positive effect of swaddling on maintaining body studies conducted / supporting information for this study temperature and reducing stress, it was concluded that it can be used as a suitable bathing method in the NICU (Edraki, M. et al.). Mohamed et al. to compare the effect of trunk-to-head bathing with traditional head- to-trunk bathing on the body temperature, heart rate, and oxygen saturation of newborns, it was found that trunk-to-head bathing had positive effects on newborns' body temperature, heart rate, and oxygen saturation compared to traditional head-to-trunk bathing. ( Mohamed , SS A et al. 2018). The results of this limited number of studies are particularly healthy and at term. There are no consistent results regarding the order in which newborns should be bathed. This suggests that there is a need for welldesigned randomized controlled studies on this subject. Based on this

babies.

literature review, this study was planned to determine the effect of bathing applied in two different orders (washing the body first and the head last, and the classical method of washing the whole body starting from the head first) on stress level, physiological parameters and crying duration in term

Publication policy	The research will be carried out in line with universal ethical principles. Parents of babies who meet the sample selection criteria will be interviewed and informed about the purpose and scope of the research, and their written consent will be obtained. Babies of parents who agree to participate in the study and who meet the sample selection criteria will be included in the study. The information obtained from the research will be used only as research data, the personal information of the baby and its parents will never be included, and confidentiality rules will be strictly followed.
	5

TR Istanbul University-Cerrahpaşa ID: İstanbul UCEdu

Statistical Analysis Plan: June 1, 2023 The effect of two different bathing methods on vital parameters and stress levels in preterm babies.

Clinical Trial Number: NCT06166485

BIOSTATISTICS PRELIMINARY ASSESSMENT

The thesis summary and research hypotheses of the thesis titled "The effect of bathing applied in two different orders on the stress level and physiological parameters in term babies" were examined in detail. For this purpose, mothers who applied to the gynecology clinic of Istanbul Şişli Hamidiye Etfal Training and Research Hospital, whose weight was between 2.5 and 4 kg, whose Apgar score was over 7 points, who did not have any health problems, who were healthy term babies, and who voluntarily agreed to participate in the study. and their children will be included. As a data collection tool;

- Personal information form,
- Processing time (time to get the bath done),
- Babies' calm down time,
- newborn stress scale,
- Physiological parameters (body temperature, pulse, respiration, O2 saturation) will be used.

Data from IBM SPSS Statistics Standard Concurrent User V 26 (IBM Corp. , Armonk , New York, USA) will be evaluated in the statistical package program. Descriptive statistics will be given as number of units (n), percentage (%), mean \pm standard deviation ($Mean\pm SD$), median (M), minimum (min) and maximum (max) values. Shapiro-Wilk normality test will be used to ensure that numerical variables comply with normal distribution. The appropriate hypothesis testing method planned to be used in the study was determined as "Mixed Pattern Variance Analysis" if parametric test assumptions were met. In cases where the parametric test assumptions regarding the relevant test are not met, whether there is a difference between the groups in terms of quantitative variables will be evaluated with the "Student t test" if the parametric test assumptions are met, and with the "Mann-Whitney test" if the parametric test assumptions are not met. In examining whether the quantitative variables change according to the pre-test and post-test measurement time, they will be examined with the "Paired t test" if the test assumptions are met, and with the "Wilcoxon test" if they are not met. In all hypothesis tests, the probability of Type I error will be taken as α =0.05 and a value of p<0.05 will be considered statistically significant.

Mohamed et al. $(2018)^{**}$ in their study, they investigated whether bathing applied in two different orders in term babies had an effect on stress level and physiological parameters. Differences between and within groups were calculated for body temperature (°C), heart rate (beats/ min) and oxygen saturation (%). Minimal significant change was observed in the study While the average heart rate (beats/ min) was 145 ± 16.44 points in the training group as a result of the first measurements, it was found to be 138 ± 12.12 points in the last measurement. In the control group, the first measurement was 140 ± 14.22 points and the last measurement was 139 ± 10.88 points. As a result, it was determined that there should be 86 observations in the sample with a statistical power level of 80.4% and a significance level of 5% for the calculated (f=0.128)* effect size. Considering sample loss (10%) such as dropping out of the study, it will be sufficient to work with at least 94 patients. The study was planned to include 47 people in each group.

^{*} COHEN, J., "Statistical Power Analysis for the Behavioral Sciences (Revised ed.)", 1977.

F tests - ANOVA: Repeated measures , within-between interaction

Analysis: A priori : Compute required sample size

Input: Effect size f=0.1275153

> α err prob =0.05=0.80Power $(1-\beta \text{ err prob })$ Number of groups =2Number of measurements =4 corr among rap measures =0.5Nonsphericity correction ϵ =1

Output: Noncentrality parameter λ =11.1869844

Critical F=2.6404222

numerator df = 3.0000000

denominator df = 252 =86 Total sample size

Actual power =0.8044596

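### No planned between-arm analysis uses the pre-bath value as a covariate; for H2, adjusting for it would usually add power and would give an arm difference with a confidence interval

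*SAP*

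**What the plan says.** The SAP's methods paragraph sets the main analysis: "hypothesis testing method planned to be used in the study was determined as 'Mixed Pattern Variance Analysis' if parametric test assumptions were met". If those assumptions fail, "whether there is a difference between the groups in terms of quantitative variables will be evaluated with the 'Student t test", or with Mann-Whitney where the t test's own assumptions fail. A pre-bath value appears only in the sentence on within-group change, which begins "In examining whether the quantitative variables change according to the pre-test and post-test measurement time" and leads to paired t or Wilcoxon tests.

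The SAP's power output is headed "F tests - ANOVA: Repeated measures , within-between interaction" and uses two groups, four measurements and a correlation of 0.5. The times of the four measurements are not listed.

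The Protocol (Statistical method to be applied) says that an "independent t test will be applied for the difference between two independent groups", and that, for an outcome recorded three or more times, "analysis of variance in repeated measurements (MIX ANOVA) will be applied and in case of a difference, Bonferroni will be applied to determine" where the difference lies. Neither procedure is tied to an outcome or a time.

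No covariate, baseline-adjusted model or confidence interval is named in either document. H2 in the Protocol is directional: it expects head-first bathing to affect the physiological parameters more adversely.

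**The concern.** Pulse, temperature, respiration and saturation differ between infants before any bath. If a pre-bath value is recorded, part of the post-bath variation can be predicted from it. The interaction test enters that value only as one more level of time, which amounts to subtracting it in full. The t and Mann-Whitney comparisons between arms do not use it at all. Regressing on it is usually more efficient than either.

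There is also an estimation gap. A 3-df interaction p-value gives neither the direction nor the size of the effect, and H2 asks for direction. What is at stake is some power, protection against chance pre-bath imbalance, and an interpretable arm difference. The validity of the planned test is not in question.

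**Working it through.** **Inputs from the SAP's sample-size section:** f = 0.1275153, N = 86 (43 per arm), 4 measurements, ρ = 0.5, ε = 1, α = 0.05.

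**The plan's own figure.** λ = f²·N·4/(1−ρ) = 0.1275153² × 86 × 4/0.5 = 11.187; df 3 and 252; critical F 2.6404; power 0.8045. This matches the SAP.

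**Assumptions added here:** one pre-bath and three post-bath values, equal variances, compound symmetry. ρ = 0.5 is the SAP's value; 0.3 to 0.7 is my range.

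**Method.** Let d be the arm difference at the three post-bath times, in SD units, with no difference before the bath.

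- Planned interaction: λ = (43/2)·d′[(1−ρ)(I+J)]⁻¹d
- Joint baseline-adjusted test: λ = (43/2)·d′[(1−ρ)(I+ρJ)]⁻¹d, with 3 df and denominator df from 81 (multivariate) to 249 (pooled)

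Here I is the 3×3 identity matrix and J the 3×3 matrix of ones. Each pattern is scaled so that the planned test has λ = 11.187. At ρ = 0.5 the quadratic forms are 2(d′d − (Σd)²/4) planned and 2(d′d − 0.2(Σd)²) adjusted:

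| Post-bath pattern | Planned form | Adjusted form | Adjusted λ | Adjusted power |
|---|---|---|---|---|
| Decay 1, 0.5, 0 | 1.375 | 1.6 | 11.187 × 1.6/1.375 = 13.02 | 0.853–0.865 |
| One occasion 1, 0, 0 | 1.5 | 1.6 | 11.187 × 1.6/1.5 = 11.93 | 0.818–0.832 |
| Constant 1, 1, 1 | 1.5 | 2.4 | 11.187 × 2.4/1.5 = 17.90 | 0.949–0.955 |
| Sum zero 1, 0, −1 | 4 | 4 | 11.19 | 0.790–0.804 |

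A simulation at ρ = 0.5 (6,000 runs per pattern) gave 0.849, 0.813 and 0.946 for the first three patterns with the multivariate test. Rejection under the null was 0.050 for the planned test and 0.049 for the adjusted one.

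**Other correlations**, again with the planned test held at 80.4%:

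| Pattern | ρ = 0.3 | ρ = 0.7 |
|---|---|---|
| Decay | 0.893–0.904 | 0.823–0.836 |
| One occasion | 0.839–0.852 | 0.804–0.818 |
| Constant | 0.987–0.989 | 0.890–0.901 |
| Sum zero | 0.790–0.804 | 0.790–0.804 |

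**Infants needed for 80.4% power** (multivariate df, ρ = 0.5): 78 for decay, 84 for one occasion, 58 for constant and 90 for sum zero, against 86 planned. At ρ = 0.7 the one-occasion pattern needs 88.

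**Why a joint test should decide.** At ρ = 0.5, an adjusted test at one chosen time has power 0.902, 0.370 or 0.050 under decay, depending on whether the first, second or third post-bath time was chosen. The adjusted post-bath mean has 0.987 for a constant effect, but 0.589 for decay and 0.286 for one occasion.

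**Precision, using the SAP's heart-rate SDs and one post-bath value.** Pooled last-measurement SD = √((12.12² + 10.88²)/2) = 11.52, so the variance is 132.6. Adjusted at ρ = 0.5 it is 132.6 × 0.75 = 99.5. With 43 per arm, the 95% half-width falls from 4.94 to 4.28 beats/min.

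**Illustration of imbalance.** The SAP gives 145 then 138 for the source study's training group, and continues: "In the control group, the first measurement was 140 ± 14.22 points and the last measurement was 139 ± 10.88 points". The contrast in change is (145−138) − (140−139) = 6 beats, of which 145 − 140 = 5 is the gap at first measurement. The pooled first-measurement SD is √((16.44² + 14.22²)/2) = 15.37. The adjusted difference is 1 + 0.5 × (11.52/15.37) × 5 = 2.9 beats (2.1 at ρ = 0.3, 3.6 at ρ = 0.7).

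**The case against.** The strongest reply is that nothing here is wrong: the test that was sized is the main test that is planned, and choosing between two valid analyses is close to preference. That stands as a limit on the point. A reader might infer that the mixed ANOVA ignores the pre-bath value, is biased, or leaves the trial mis-sized. The documents support none of this, since the interaction tests differential change and its sample size reproduces exactly.

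The condition is also unconfirmed. The pre-test wording belongs to the paired tests, and the first measurement in the sample-size section describes another study. No text says that stress is scored before the bath, so extending the point to H1 is not supported.

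The 95% figure needs an effect of equal size at all three times. The Protocol's literature summary reports faster return to pre-bath temperature with trunk-to-head bathing, which fits decay better, so the decay row is the fairer guide. A reader might also infer that adjustment always gains power. It does not: when post-bath effects sum to zero there is none, and with multivariate df about 1.5 points are lost.

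For the Protocol's t test, the sizing sentence reads "Assuming that the evaluations to be made between two independent groups would have a medium effect size (d = 0.5" and is tied to no outcome. With 64 per group, power would go from 80.1% to 90.0% at ρ = 0.5, but only if the test is applied to one post-bath value that has a pre-bath counterpart.

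Two further objections stand and shape the fix. The SAP provides for failed parametric assumptions, so a parametric model cannot be the only deciding analysis. And arm differences with CIs could be reported from the planned model, so the missing interval alone would not justify changing the test.

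**Conclusion.** The point holds as a worthwhile improvement in efficiency and estimation for H2, conditional on a pre-bath value being one of the four measurements. At the SAP's own correlation the likely gain is modest: roughly 1 to 6 percentage points of power for one-occasion or decaying effects, and about 15 for a constant effect. It is essentially nil for a one-occasion effect at ρ = 0.7 and absent when post-bath effects sum to zero. The more dependable benefits are removal of chance pre-bath gaps and an arm difference with an interval that shows direction.

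The figures rest on one pre-bath and three post-bath values, compound symmetry and equal variances. The source study's heart-rate SDs (15.37 first, 11.52 last) are not equal, so the powers are indicative. Procedure time and calming time have no pre-bath value and are not affected.

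**What to change.** - State which of the four measurements are pre-bath.
- For each physiological parameter, and for stress only if it is scored before the bath, model the post-bath values with arm, time, arm-by-time and the pre-bath value as covariate. Fix the covariance structure and df method in advance. With a single post-bath time this is ANCOVA.
- Let the joint test of arm over all post-bath times decide. Report the adjusted arm difference with a 95% CI at each time as the estimate, not as a further deciding test.
- For an outcome that fails parametric assumptions (saturation, a bounded percentage, is a candidate), name the deciding analysis in advance: either a baseline-adjusted rank-based or transformed version of the same model, or the planned Mann-Whitney comparison.
- Keep the mixed ANOVA as supportive.

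The cost is wording in the SAP and Protocol. No infants or measurements are added, and the model is available in the planned software. The downside is the possible loss of about 1.5 power points in the sum-zero pattern if multivariate df are used.
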